**Protocol Amendment 1.1**

1. Section 6.0, Table 1: Added and removed variables

**Protocol Amendment 1.2**

1. Section 6.0, Table 1: Variables moved to Appendix 3
2. Appendix 3: added variables

**Protocol Amendment 1.3**

1. Change inclusion/exclusion criteria and study design to be more flexible and accurately capture cardiac surgery patient population.

## 1.0 INTRODUCTION AND BACKGROUND

Cardioplegia was first introduced as a method to protect the heart during cardiac surgery in the 1950s (1). Initially, it consisted of a crystalloid solution and in the 1970s Follette and colleagues proposed that blood was the best mode of delivery of cardioplegia as it is rich in nutrients and oxygen (2). Blood has better osmotic, buffering, and antioxidant qualities that are needed by ischemic myocardium. More recent studies comparing blood and crystalloid cardioplegias showed that there was less cardiac edema, and recovery of ventricular function was more rapid with blood based cardioplegia (3). A meta-analysis of over 5000 patients corroborated these findings and showed that blood based cardioplegia reduced the incidence of postoperative low cardiac output syndrome and was associated with less myocardial damage (4).

Standard diluted blood cardioplegia can also be modified to undiluted blood cardioplegia also known as microplegia. To compare the cardioprotection of 4:1 blood:crystalloid cardioplegia to microplegia, McCann et al randomized 20 pigs to either group. Cardiac edema was measured using histologic morphometrics and echocardiogram. It was noted that both edema percentage and left ventricular mass were significantly more decreased in the microplegia group. Furthermore, all animals receiving microplegia were successfully weaned off cardiopulmonary bypass, whereas only 40% of those receiving standard cardioplegia were successfully weaned (5).

More recently, Algarni *et al.* showed decreased prevalence of low cardiac output syndrome in patients who received microplegia (n=2,630) (6). Another study compared microplegia and standard cardioplegia in patients undergoing coronary artery bypass grafting and found that the microplegia group had lower troponin levels during the post-operative course. Moreover, microplegia resulted in lower transfusion rates and decreased length of hospital stay (7).

A high rate of patients undergoing cardiac surgery require red blood cell transfusions (RBC). Red blood cell transfusions are strongly associated with both infection and ischemic postoperative morbidity, length of stay, increased early and late mortality, and overall hospital costs (8). Given that previous studies have shown that microplegia is associated with less transfusions, it would be reasonable to incorporate this into practice at Washington University.

## 2.0 HYPOTHESIS AND AIMS

The hypothesis is that diluted 4:1 cardioplegia used in adult cardiac surgery at Washington University in St. Louis contributes to increased transfusion rates peri-operatively and incorporation of Quest, Inc. microplegia may decrease RBC transfusion rates, and thus, impact overall morbidity and mortality after cardiac surgery.

Specific aims are:

1. To determine if use of microplegia results in less peri-operative transfusions compared to diluted 4:1 cardioplegia.
2. To investigate the effects of microplegia on overall morbidity and mortality during the peri-operative period. We will assess operative mortality and 30 day mortality. We will examine intra-operative and post-operative complications. A complete list of variables to be examined can be found in table 1. We will determine if microplegia results in better myocardial protection than standard cardioplegia by assessing pre-operative, intra-operative and post-operative serum troponin levels.

### **3.0 INCLUSION CRITERIA**

Patients must meet all of the following criteria to be considered eligible for study participation:

1. Are to undergo non-emergent cardiac surgery
2.  $\geq 18$  years of age.
3. Willing and able to provide informed consent.

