### **4.0 EXCLUSION CRITERIA**

Patients must not meet any of the following criteria to be considered eligible for study participation:

1. History of endocarditis.
2. Dialysis-dependent renal failure.
3. Currently on pre-operative mechanical circulatory support (i.e. ECMO, LVAD or intra-aortic balloon pump [IABP]).
4. Contraindication to receiving a blood transfusion (i.e. Jehovah's Witness).
5. Emergent procedures.

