### **5.0 STUDY DESIGN**

The hypothesis will be accomplished in a randomized, blinded, prospective institutional study conducted at two sites, Barnes Jewish Hospital and Christian Northeast Hospital. 314 patients will be randomized to either receive diluted 4:1 cardioplegia or nondiluted microplegia. This will be a blinded study to both the patient and surgeon. The patient will be randomized during the preoperative period. Quest Medical Inc. will supply us with the microplegia MPS-2 machines needed to conduct this study. Outcomes will be measured by a blinded clinician.

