## **9.0      STATISTICAL ANALYSIS**

Continuous variables will be expressed as mean  $\pm$  standard deviation or as median with range. Categorical variables will be expressed as frequencies and percentages with outcomes compared using the  $\chi^2$  or the Fisher exact test. Continuous outcomes will be compared using the *t* test for means of normally distributed continuous variables and the Mann-Whitney U nonparametric test for skewed distributions. Significant covariates on univariate analysis ( $p \leq 0.10$ ) or covariates deemed clinically relevant based on experience will be entered into a multivariate binary logistic regression analysis.

A sample size of 314 patients will be randomized to either receive standard 4:1 cardioplegia or microplegia. The sample size was calculated based on a one tailed test with alpha 0.05 and beta 0.2 (80% power) to detect a 25% relative risk reduction in pRBC units transfused. An interim analysis will be completed following the enrollment of 150 patients.

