## 15.0 Appendix 3: Data Collection

**Table 1:** Baseline pre-operative, operative, and post-operative variables to be examined.

Pre-operative variables	Intra-Operative Variables	Post-Operative Variables
Age	pRBC transfusion (see appendix 2, peri-operative transfusion form): date, number of units, name of staff ordering transfusion, actual/predicted hematocrit, justification if hematocrit >20%	pRBC transfusion (see appendix 2, perioperative transfusion form): date, number of units, name of staff ordering transfusion, hemoglobin level, justification if hemoglobin $\geq 7.0$ g/dL.
Weight	Platelet transfusion: number of units	Platelet transfusion: number of units
Dyslipidemia	FFP transfusion: number of units	FFP transfusion: number of units
Hypertension	Mortality	Hematocrit on arrival to ICU
COPD	Clamp time	Hematocrit 24 hours post-operatively
Coronary artery disease	Amount of cardioplegia/microplegia delivered	30 day mortality
Liver disease	Type of surgery	Time on ventilator
Cerebrovascular disease	CPB time	Hours in the intensive care unit
Previous cardiac interventions	Cross-clamp time	Length of hospital stay
History of arrhythmia	Cardioplegia technique	Renal failure
Diabetes mellitus	Number of grafts	Pulmonary complications
LVEF (%)	Concomitant procedures	Low output syndrome
Congestive heart failure	Pre-CPB hematocrit	Myocardial infarction
Peripheral vascular disease	On-CPB hematocrit	Serial troponins: arrival to ICU, 12 and 24 hours post-op
Hemoglobin, hematocrit	Post-CPB hematocrit	New onset post-op atrial fibrillation
Creatinine	Date of surgery	Stroke
Troponin	Skin incision to skin close time	Mortality
Previous PCI +/- stents	Cardioplegia Delivery	Readmission
Angina	Additive Volume	Readmission date
BMI	Arrest Agent Volume	Readmission reason
Height	Total CDPG	
Ethnicity	Crystalloid Amount	
Race	Crystalloid Total	
Chronic Lung Disease	Anesthesiologist	
Immunocompromise	Perfusionist	
Mediastinal Radiation	Starting glucose	

Thoracic Aorta Disease	Final glucose	
Sex	TEE score	
Date of admission	Time to arrest	
	Volume to arrest	
	Cryoprecipitate volume	Cryoprecipitate volume

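### Mixed case mix at two hospitals: no stratification is specified, and the planned comparison of pRBC units adjusts for neither operation type nor hospital, which costs power

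*Combined protocol and SAP*

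**What the plan says.** - **Eligibility.** Section 3.0 requires that adults "Are to undergo non-emergent cardiac surgery". The Section 4.0 exclusions concern patient states, such as "Currently on pre-operative mechanical circulatory support", and emergent cases. None removes a type of elective operation.
- **Sites and allocation.** Section 5.0 describes a "prospective institutional study conducted at two sites". It states that "314 patients will be randomized to either receive diluted 4:1 cardioplegia or nondiluted microplegia" and that "The patient will be randomized during the preoperative period". Ratio, blocks, strata and concealment are not described.
- **Analysis.** Section 9.0 plans a t test or Mann-Whitney test for continuous outcomes and a chi-square or Fisher test for categorical ones. Covariates with a univariate p of 0.10 or less, or judged clinically relevant, go into a multivariable binary logistic regression. No covariate is named, and the model is not designated as primary.
- **Sample size.** Section 9.0 bases 314 on a 25% relative reduction in pRBC units, using a "one tailed test with alpha 0.05 and beta 0.2 (80% power").
- **Data.** Table 1 (Appendix 3) lists type of surgery and "Concomitant procedures" among the intra-operative variables. Hospital is not listed.

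**The concern.** Open eligibility mixes operations whose transfusion needs probably differ. Part of the spread in units would then come from operation type, which is known before assignment and has nothing to do with cardioplegia. An unadjusted test leaves that spread in the error term. The logistic model does not solve this: it needs a yes/no outcome, whereas the sample size is framed in units. Selecting covariates partly by p-value also leaves the adjusted analysis undefined until the data are seen. Hospital could not reliably enter any model, because the plan does not list it for collection.

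At stake is power for the 25% target. A marked imbalance in complex cases, should one occur, would also make the unadjusted estimate hard to interpret.

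**Working it through.** **The plan's own figure.** The inputs in Section 9.0 do not determine 314, because no control mean, standard deviation or transfusion rate is given. For a difference in means, with CV the coefficient of variation of units,

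n per arm = 2 × CV² × (1.645 + 0.842)² / 0.25².

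With CV = 0.89: 2 × 0.792 × 6.18 / 0.0625 ≈ 157, so 314 in total. If the endpoint is read as a proportion transfused, 314 corresponds to a control rate of about 0.56 (one-sided, no continuity correction).

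**Assumptions.** The documents give no case mix or unit means. I assume:
- 1:1 allocation, so 157 per arm;
- 40% complex operations;
- control means of 3 units (complex) and 1 unit (other);
- within-class variance of 2, 4 or 6.

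The control mean is 0.4 × 3 + 0.6 × 1 = 1.8 units, and a 25% reduction is 0.45 units. The between-class variance is 0.4 × 0.6 × (3 − 1)² = 0.96.

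**Power for units.** Power = Φ(0.45 / (SD × √(2/157)) − 1.645), where √(2/157) = 0.1129. The SD is √(within + 0.96) without adjustment and √within with adjustment. This is a normal approximation.

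| Within-class variance | SD, unadjusted | Power, unadjusted | SD, adjusted | Power, adjusted |
|---|---|---|---|---|
| 2 | 1.72 | 75% | 1.41 | 88% |
| 4 | 2.23 | 56% | 2.00 | 64% |
| 6 | 2.64 | 45% | 2.45 | 49% |

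The gain is about 5 to 13 points.

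**Power for a yes/no endpoint.** This was simulated with 100,000 trials per scenario, 157 per arm and one-sided 0.05. The assumed high-risk share was 30–50%, with transfusion risk 35–45% in the low-risk and 60–75% in the high-risk stratum.

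| Allocation and test | Power | False-positive rate |
|---|---|---|
| Simple, unadjusted | 69–79% | 4.9–5.1% |
| Simple, Mantel-Haenszel | 71–83% | 5.0–5.1% |
| Stratified, Mantel-Haenszel | 71–84% | 5.0% |

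The gain is about 1 to 5 points, and the second row shows that adjustment alone provides nearly all of it. Stratified allocation followed by an unadjusted test was conservative, with a false-positive rate of 3.6–4.9%. If the list is stratified, the analysis therefore needs the same factors.

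**Chance imbalance under simple randomisation.** With a 40% share, the SD of the between-arm difference is √(0.4 × 0.6 × 2/157) = 0.055. The probability of a difference of 10 points or more, in either direction, is 2 × (1 − Φ(0.10/0.055)) ≈ 7%. At the planned interim look (75 per arm) the SD is 0.080 and the probability about 21%. A 10-point imbalance moves the mean difference by 0.10 × 2 = 0.2 units, against the 0.45 sought.

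In the yes/no simulation, among trials with more than 10 points of imbalance, the unadjusted false-positive rate was 11–21% when the imbalance favoured microplegia. Power was 51–59% when it went against microplegia.

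**The case against.** **The plan already adjusts.** Section 9.0 admits clinically relevant covariates, and Table 1 collects type of surgery, concomitant procedures and number of grafts. So adjustment is not absent. It is, however, unnamed, not primary, partly driven by p-values and confined to a binary outcome.

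**Transfusion is standardised.** Appendices 1 and 2 set transfusion criteria for the whole study and require deviations to be justified. That stands. The documents show no difference in practice between hospitals, so I put no number on the hospital factor. Including it is a low-cost precaution.

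**Broad eligibility is deliberate.** Amendment 1.3 widened the criteria to reflect the cardiac surgery population, and Section 2.0 asks about adult cardiac surgery. This also stands. Section 1.0 notes that "Another study compared microplegia and standard cardioplegia in patients undergoing coronary artery bypass grafting", and the other cited human microplegia study is also in bypass patients. A reader might infer that the trial should be restricted to bypass or made comparable with that literature. That is a preference; population and question match.

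**Stronger readings that the documents do not support.**
- A reader might infer that randomisation is unstratified. Section 5.0 is silent on the method, so one can say only that no stratification is specified.
- A reader might infer that imbalance will mask or mimic an effect. Randomisation keeps the overall error rate at about 5%. Distortion arises only given a marked imbalance, which is uncommon at 314, and only about half of such imbalances favour microplegia.
- A reader might apply the variance reduction to the planned 80% and expect 85% to 92%. Under the same assumed means and variances, unadjusted power is 75%, 56% or 45%, so that starting point does not hold.

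**Conclusion.** The point holds as a question of efficiency and pre-specification, not of validity. With open eligibility and two hospitals, the plan compares its powered quantity by unadjusted tests and offers a covariate model that cannot be applied to it. Under the stated assumptions, adjusting for operation type is worth about 5 to 13 points of power on units, or about 1 to 5 points on yes/no transfusion. Stratified allocation is sound but adds little power; its use is to secure balance, particularly at the interim look.

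The size depends on the assumed case mix, unit means and 1:1 ratio. With a smaller gap between operation types the gain shrinks. The unstated control mean and SD behind 314 matter more for power than this point does, but that is a separate matter. I would make the change because it is cheap and because stratified allocation cannot be added afterwards.

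**What to change.** 1. **Section 9.0.** Make the primary comparison of pRBC units one that includes planned operation (isolated coronary bypass versus other) and hospital as factors fixed in advance and not selected by p-value. A rank test stratified by both, or a count regression with both terms, would serve. Name one.
2. **Table 1.** Add hospital, and planned operation recorded before assignment. The existing type-of-surgery item sits among the intra-operative variables and does not replace it.
3. **Section 5.0.** State the allocation ratio, and stratify the list by the same two factors in permuted blocks.

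**Cost.** A sentence each in Sections 5.0 and 9.0, two data fields and a stratified list. Four strata average about 78 patients each (314/4), which is workable. The protocol names REDCap as the database only, so the randomisation tool must be confirmed. The downside is that planned operation must be entered before assignment, and patients whose final operation differs stay in their planned stratum.

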### **4.0 EXCLUSION CRITERIA**

Patients must not meet any of the following criteria to be considered eligible for study participation:

1. History of endocarditis.
2. Dialysis-dependent renal failure.
3. Currently on pre-operative mechanical circulatory support (i.e. ECMO, LVAD or intra-aortic balloon pump [IABP]).
4. Contraindication to receiving a blood transfusion (i.e. Jehovah's Witness).
5. Emergent procedures.

### **5.0 STUDY DESIGN**

The hypothesis will be accomplished in a randomized, blinded, prospective institutional study conducted at two sites, Barnes Jewish Hospital and Christian Northeast Hospital. 314 patients will be randomized to either receive diluted 4:1 cardioplegia or nondiluted microplegia. This will be a blinded study to both the patient and surgeon. The patient will be randomized during the preoperative period. Quest Medical Inc. will supply us with the microplegia MPS-2 machines needed to conduct this study. Outcomes will be measured by a blinded clinician.

#### ***Microplegia***

The microplegia machine to be used for all study subjects is the FDA approved MPS2 Microplegia delivery machine manufactured and distributed by Quest Medical, Inc.

The microplegia solution that is standard of care for all cardiac surgery patients, and which all study subjects will receive is:

#### **Induction**

240 mL Baxter Cardioplegia Solution

10.5 mL Potassium Chloride 2 meq/ml (21 meq)

250.5 mL total volume

#### **Maintenance**

747 mL Baxter Cardioplegia Solution

3.4 mL Potassium Chloride 2 meq/ml (6.75 meq)

750.4 mL total volume

Subjects will be randomly assigned to 4:1 cardioplegia or nondiluted microplegia.

4:1 cardioplegia consists of 4 parts crystalloid intravenous fluid to one part human blood.

Nondiluted microplegia consists of all parts human blood.

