**7.0 RISKS**

All microplegia will be delivered using the MPS-2 Myocardial Protection System. This is an approved device currently used in many cardiac centers worldwide. There is no change in risk that can be associated with the use of microplegia versus standard cardioplegia currently used as standard of care.

Blood drawing poses the following risks: pain, bleeding, or bruising and rarely, infection. All peri-operative blood draws can be performed while the subject has a standard of care intravenous line in place. There will be no needle sticks required.

There is a rare risk of breach of confidentiality of study data.

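### Section 5.0 defines the control's 4:1 cardioplegia as four parts crystalloid to one part blood, the reverse of the protocol's only other ordered use of the label, and is probably transposed

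*Combined protocol and SAP*

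**What the plan says.** Section 5.0, at the end of the text under Maintenance, defines the control: "4:1 cardioplegia consists of 4 parts crystalloid intravenous fluid to one part human blood". No other sentence states what the control mixture contains. The next sentence describes nondiluted microplegia as blood throughout.

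Section 1.0 gives the order of the label once, when it introduces an experiment in 20 pigs: "To compare the cardioprotection of 4:1 blood:crystalloid cardioplegia to microplegia". The sentence before sets the context: "Standard diluted blood cardioplegia can also be modified to undiluted blood cardioplegia also known as microplegia". When the result is reported, the 4:1 arm is simply standard cardioplegia: "whereas only 40% of those receiving standard cardioplegia were successfully weaned".

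The remaining references to the trial's control give no order:

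- Section 2.0, hypothesis: "diluted 4:1 cardioplegia used in adult cardiac surgery at Washington University in St. Louis". Specific aim 1 also says only diluted 4:1.
- Section 5.0, opening paragraph: "314 patients will be randomized to either receive diluted 4:1 cardioplegia or nondiluted microplegia". The random assignment sentence under Maintenance says only 4:1.
- Section 7.0: "the use of microplegia versus standard cardioplegia currently used as standard of care", without the ratio.
- Section 9.0: "A sample size of 314 patients will be randomized to either receive standard 4:1 cardioplegia or microplegia".

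Section 5.0 also lists an induction and a maintenance solution of Baxter cardioplegia solution and potassium chloride, which every subject is to receive. Appendix 3, Table 1 records the amount of cardioplegia delivered and the crystalloid, additive and arrest agent volumes. It prescribes none of them.

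**The concern.** The hypothesis in Section 2.0 is that diluting the cardioplegia contributes to red cell transfusion. Dilution is therefore the exposure, and the crystalloid share of the control sets how large that exposure is. The one sentence that fixes this share gives the opposite order from the comparator that the protocol uses to motivate the trial, although both carry the name standard cardioplegia.

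Two things are at stake. First, the protocol is the common specification for two hospitals, and a site that followed Section 5.0 to the letter would give a far more dilute control than the background describes. Second, a later reader or meta-analyst who takes the definition at face value would misclassify the comparator if the ratio is transposed. If the ratio is not transposed, the background evidence concerns a much less diluted comparator than the one under test, and the protocol does not say so.

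**Working it through.** **Step 1. Compare the uses of the label.**

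| Place | Subject | Order given |
|---|---|---|
| 1.0 | Cited pig study, 4:1 arm | Blood to crystalloid |
| 2.0, hypothesis and aim 1 | Trial control | None |
| 5.0, opening paragraph | Trial control | None |
| 5.0, random assignment sentence | Trial control | None |
| 5.0, definition | Trial control | Crystalloid to blood |
| 9.0 | Trial control | None |

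Only two uses give an order, and they are opposite. The Section 5.0 order is written out in words, so it is not an artefact of how a ratio was typeset or read from the PDF.

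**Step 2. Turn the ratios into shares.** For a parts crystalloid and b parts blood, the crystalloid share is a/(a + b) and the blood share is b/(a + b).

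- Section 5.0 (a = 4, b = 1): crystalloid 4/5 = 80%, blood 1/5 = 20%. Per 1000 mL delivered: 800 mL crystalloid and 200 mL blood.
- Section 1.0 order (a = 1, b = 4): crystalloid 1/5 = 20%, blood 4/5 = 80%. Per 1000 mL delivered: 200 mL crystalloid and 800 mL blood.

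The crystalloid shares differ by a factor of 80/20 = 4, or 80 − 20 = 60 percentage points. The blood share under Section 5.0 is 20/80 = one quarter of that under Section 1.0.

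**Step 3. See whether the listed recipe settles the order.** Induction: 240 + 10.5 = 250.5 mL. Maintenance: 747 + 3.4 = 750.4 mL. Both agree with the stated totals, so the recipe is consistent as a list of stock ingredients. It gives no proportion for mixing with blood, so it favours neither order.

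**Step 4. See whether the terminology settles it.** Section 1.0 presents the pig study straight after contrasting standard diluted blood cardioplegia with microplegia, and calls the 4:1 arm standard. Section 9.0 calls the trial's control standard 4:1 cardioplegia. Section 7.0 calls it standard cardioplegia in current use, and Section 2.0 says 4:1 cardioplegia is what the institution uses. The shared name points to one mixture and so to a transposition in Section 5.0. This is an inference from naming, because no sentence equates the two mixtures.

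The protocol prescribes no delivered volume per patient, so the difference can be given only per litre.

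**The case against.** The strongest reply is that nothing said about this trial contradicts Section 5.0. The ordered ratio in Section 1.0 describes a cited animal experiment, and every other mention of the trial's control is silent on order. The word standard is generic: Section 1.0 also uses it for a coronary bypass study for which no ratio is given. This stands to the extent that a reader might infer a proven error, and the documents do not go that far. It does not remove the point. The protocol brings in the pig study to represent the comparison it goes on to test, so a comparator of very different composition would need a sentence of explanation, and there is none.

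A second reply is that the consequence is small. The control is existing practice, so perfusionists may already deliver the intended ratio whatever the text says, and the recorded volumes will show what was given. Both statements are fair. A reader might infer from Section 5.0 that control patients actually received 80% crystalloid, and the documents do not support that. However, recorded volumes show what was delivered, not what was intended, and the intention is what is unclear.

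A reader might also infer that microplegia described as entirely blood cannot be reconciled with a Baxter and potassium chloride solution given to everyone. The documents do not support this. Section 1.0 defines microplegia as undiluted blood cardioplegia, and Table 1 records additive and arrest agent volumes, so additives are plainly expected. The natural reading is a common stock used differently in the two arms. What remains is a missing detail: the additive proportion in the microplegia arm.

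**Conclusion.** The concern holds as a mismatch in the definition of a randomised arm. As written, the control is 80% crystalloid, against 20% in the protocol's only other ordered use of the label: four times the crystalloid share and a quarter of the blood share. That the two orders are opposite is certain from the text. That Section 5.0 is the one in error is likely but unproven. It rests on the assumption that standard cardioplegia means the same mixture in the background and in the trial.

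The direction of the contrast, diluted against undiluted, is clear under either order. The sample size and the planned tests do not use the ratio, so they are unaffected. The documents do not show that any patient was given the wrong mixture. The sentence should still be corrected, because it specifies the exposure under test and can be put right cheaply.

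**What to change.** Ask the perfusion team at both sites which ratio is used as standard of care. Then amend the definition in Section 5.0 to state it with the order explicit. The expected wording is four parts blood to one part crystalloid. If four parts crystalloid to one part blood is truly intended, keep it, say that it is deliberate, and explain why the control departs from the comparator in Section 1.0.

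As an optional clarification in the same amendment, state that the Baxter and potassium chloride recipe is the stock solution, and give the additive proportion in the microplegia arm.

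The cost is one confirmation and a wording amendment. Sample size and analysis stay as they are. Procedures also stay as they are if current practice already follows the intended ratio.
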